**LIST OF ABBREVIATIONS AND RELEVANT DEFINITIONS**

AE	Adverse Event
AR	Adverse Reaction
BMI	Body Mass Index
CA	Competent Authority
CGM	Continuous Glucose Monitoring
COVID-19	Coronavirus
CV	Curriculum Vitae
DM	Diabetes Mellitus
DSMB	Data Safety Monitoring Board
DSMQ-R	Diabetes Self-Management Questionnaire
EU	European Union
EudraCT	European drug regulatory affairs Clinical Trials
FGM	Flash Glucose Monitoring
FSL	FreeStyleLibre
GCP	Good Clinical Practice
GDPR	General Data Protection Regulation; in Dutch: Algemene Verordening Gegevensbescherming (AVG)
HbA1c	Glycated Hemoglobin
IB	Investigator's Brochure
IC	Informed Consent
IMP	Investigational Medicinal Product
IMPD	Investigational Medicinal Product Dossier
LUMC	Leiden University Medical Center
METC	Medical research ethics committee (MREC); in Dutch: medisch-ethische toetsingscommissie (METC)
NA	Not Applicable
PAID	Problem Areas In Diabetes
PI	Principal investigator
PSS	Perceived Stress Scale
QoL	Quality of Life
(S)AE	(Serious) Adverse Event
SDSCA	Summary of Diabetes Self-Management Activities
SMBG	Self-monitoring of Blood Glucose
SPC	Summary of Product Characteristics; in Dutch: officiële productinformatie

	IB1-tekst
Sponsor	The sponsor is the party that commissions the organisation or performance of the research, for example a pharmaceutical company, academic hospital, scientific organisation or investigator. A party that provides funding for a study but does not commission it is not regarded as the sponsor, but referred to as a subsidising party.
SUSAR	Suspected Unexpected Serious Adverse Reaction
T1DM	Type 1 Diabetes Mellitus
T2DM	Type 2 Diabetes Mellitus
UAVG	Dutch Act on Implementation of the General Data Protection Regulation; in Dutch: Uitvoeringswet AVG
WHO-5	Well-being questionnaire
WMO	Medical Research Involving Human Subjects Act; in Dutch: Wet Medisch-wetenschappelijk Onderzoek met Mensen

## SUMMARY

**Rationale:** Diabetes mellitus is a chronic disease characterized by the inability of the body to maintain normoglycemia. Treatment of diabetes relies mostly on diabetes self-management, requiring a large investment of time and energy on a daily basis. Psychological wellbeing, behavioral patterns and social context have shown to play a major role in diabetes-self-management and glycemetic control. Self-quarantining may impact glycemetic control by influencing daily routines, self-measurement behavior, therapy adherence, physical activity and eating behaviors. A period of nationwide self-quarantine, such as during the outbreak of COVID-19 in the Netherlands, therefore may have a large effect on glycemetic control in patients with diabetes.

**Objective:** We aim to assess the impact of long-term self-quarantine on glycemetic control, diabetes self-management and distress in patients with type 1 diabetes mellitus (T1DM) and type 2 diabetes mellitus (T2DM).

**Study design:** This is an observational cross sectional study in Dutch patients with diabetes mellitus in tertiary care after self-quarantine for at least 6 weeks as result of the COVID-19 pandemic. Patients treated at the diabetes outpatient clinic of the Leiden University Medical Center (LUMC) will be approached for potential study participation. Measurements will be performed during the quarantine period or as soon as possible after. Patients will be asked to perform a fingerprick for HbA1c measurement once, which they can send back to the LUMC by mail. In addition, data from continuous glucose monitoring (CGM) or flash glucose monitoring (FGM) devices will be collected according to standard clinical practice. Furthermore, patients will be asked to fill out an online questionnaire once on diabetes self-management behaviour, well-being and distress, along with questions about health status, level of education, medication use, employment, social situation and the impact of self-quarantine on daily routines.

Data on demographics, type of diabetes, weight, BMI and HbA1c prior to the COVID-19 outbreak will be derived from the electronic health dossier of the patient. The most recent HbA1c will be used for data analysis.

**Study population:** Patients with T1DM and T2DM that are currently in care at the outpatient diabetes clinic of the LUMC are eligible for participation.

**Intervention (if applicable):** NA

**Main study parameters/endpoints:** The main study parameter is glycemetic control in patients with T1DM and T2DM assessed by HbA1c. We will also determine the change in HbA1c per patient group, as well as glucose variability, assessed by the standard deviation of glucose values in patients wearing continuous and flash glucose sensors, and the change in glucose variability before and after the nation-wide self-quarantine phase for COVID-19. In

addition, self-management, well-being and distress will be measured, using the DSMQ-R, SDSCA, WHO-5, PSS and PAID questionnaire.

**Nature and extent of the burden and risks associated with participation, benefit and group relatedness:**

The risks associated with participation in this study are limited. The primary potential foreseeable risk associated with participation in this study is negative feelings resulting from the increased attention to the patient's illness and distress by filling out the questionnaires. Additionally, there is a limited burden of time for the patient for performing the fingerprick and filling out the questionnaires, however, this time is limited and the measurement is being performed only once. Performing the fingerprick may be another foreseeable risk, however, for most patients performing a fingerprick for measurement of blood glucose values is already part of their regular daily routine.

## 1. INTRODUCTION AND RATIONALE

In the early Spring of 2020 the worldwide pandemic viral outbreak of COVID-19 caused a rapid increase in morbidity and mortality especially in patients. In an attempt to control the outbreak, many countries implemented forms of mass quarantine. Quarantine strategies diverged from total lock-down of cities or countries, voluntary home curfews, travel restrictions and prohibition of public and social events (1). In all affected countries these strategies required major adaptations of behavioral patterns, social activities and employment of the population.

Such sudden and major disruptions from every-day-life are known to influence both mental and physical health. Recent studies describing the psychological impact of quarantine, showed that experiencing quarantine is related to a wide range of stress and mood related symptoms, such as depression, anxiety, irritability, poor concentration, insomnia and post-traumatic stress disorder (PTSD)(1, 2). Longer periods of quarantine have been associated with increased chances of developing PTSD. In addition, several studies suggest that such symptoms might even last long after ending quarantine (1, 2).

Recent studies and global media suggest that individuals with diabetes mellitus (DM) are at higher risk for complications and death from COVID-19 (3). Especially patients with T2DM, who are frequently overweight and have other comorbidities such as hypertension and cardiovascular disease are at a high risk for a complicated course of COVID-19 (4). People with diabetes and their relatives may therefore experience increased feelings of stress, fear and anxiety regarding the risk of being infected with the coronavirus. And additionally, they may put even greater emphasis on the importance of self-quarantine.

Emotional distress as well as changes in daily structures and behaviors are known to influence diabetes self-management and glycemetic control (5-8). Maintaining glycemetic control during self-quarantine can therefore be challenging. Alterations in physical activity, diet and daily patterns may result in an imbalance between blood glucose values and the amount of insulin injected or other drugs prescribed, resulting in glycemetic dysregulation (9-11).

Furthermore, feelings of anxiety or distress towards the situation may further increase blood glucose values and add to the psychological burden of disease (5-8, 12).

The current study aims to assess the impact of self-quarantine on glycemetic control in patients with type 1 and type 2 diabetes. In addition, this study describes diabetes self-management, well-being and distress in Dutch patients with type 1 and type 2 diabetes, during a nationwide period of self-quarantine.

It is hypothesized that experiencing this period of nationwide quarantine influences glycemetic control and that patients reporting severe distress or low well-being experience more

problems in regard to diabetes self-management and maintaining glyceimic control than those without psychological distress or low well-being (13).

Research hypotheses:

H1: Experiencing self-quarantine impacts glyceimic control and glucose variability

H2: a) Experiencing high levels of distress is related to (poorer) glyceimic control

H2: b) Experiencing low levels of well-being is related to (poorer) glyceimic control

H3: a) Experiencing high levels of distress is related to suboptimal diabetes self-management

H3: b) Experiencing low levels of well-being is related to suboptimal diabetes self-management

H4: Experiencing self-quarantine impacts HbA1c, glucose variability, well-being, distress and self-management more in patients with type 1 than in patients with type 2 diabetes

## 2. OBJECTIVES

### Primary Objective:

- To determine the effect of a period of nationwide self-quarantine on glycemc control, assessed by HbA1c, in patients with type 1 and type 2 diabetes

### Secondary Objective(s):

- To determine the effect of a period of nationwide self-quarantine on glucose variability assessed by the standard deviation (SD) of glucose values (glucose variability) in patients with type 1 and type 2 diabetes
- To assess the association between well-being and glycemc control during a period of nationwide self-quarantine. Well-being will be measured by the WHO-5.
- To assess the association between (diabetes) distress and glycemc control during a period of nationwide self-quarantine. (Diabetes) distress will be measured by 'Perceived Stress Scale'(PSS) and 'Problem Areas in Diabetes' (PAID).
- To assess the association between diabetes self-management and glycemc during a period of nationwide self-quarantine. Self-management behaviour will be measured by the 'Summary of Diabetes Self-Care Activities' (SDSCA) and 'Diabetes Self-Management Questionnaire-rev.' (DSMQ-R)
- To determine differences HbA1c, glucose variability, well-being, distress and self-management between patients with type 1 and type 2 diabetes

### 3. STUDY DESIGN

This study is an observational, cross sectional study to assess the impact of self-quarantining on glyceimic control, diabetes self-management, distress and well-being. Patients with type 1 and type 2 diabetes mellitus currently in care at the diabetes outpatient clinic of the LUMC will be eligible to participate and will receive information about this study and an informed consent form. A few days later they will be contacted by phone to resolve any questions they may have and ask if the patient wants to participate in the study. If patients want to participate, they will sign the informed consent form and send it to the LUMC by mail. Once informed consent is provided, patients will be sent an envelope including a fingerprick device and a small tube. They will be asked to fill the tube with several drops of blood up to a mark on the tube and send the envelope back to the LUMC postage free. At the LUMC the HbA1c will be measured by the clinical chemistry lab. If the patients wears a continuous or FSL sensor, sensor data will be collected according to standard clinical practice. Furthermore, patients will receive a link by e-mail to a set of online questionnaires, containing the DSMQ-R, SDSCA, PSS, PAID and WHO-5, along with questions about level of education, medication use, employment, social situation and the impact of self-quarantine on daily routines. The HbA1c measurement and questionnaire will be performed at least 6 weeks after starting the quarantine period but still within a period of quarantine measures. Questionnaires will assess the extent and impact of the quarantine measures for each individual patient and assess the effect on glyceimic control, distress and well-being. Data on HbA1c measurements in the 12 months prior to the period of nationwide self-quarantine will be retrieved from the electronic health record of each patient, if available.

## 4. STUDY POPULATION

### 4.1. Population (base)

Patients with type 1 diabetes and type 2 diabetes will be recruited from the diabetes outpatient clinic of the LUMC.

### 4.2. Inclusion criteria

In order to be eligible to participate in this study, a subject must meet all of the following criteria:

- Age  $\geq$  18 years
- Diagnosed with type 1 or type 2 diabetes
- Ability to perform fingerpricks
- Sufficient comprehension of the Dutch language
- Ability to fill out online questionnaires

### 4.3. Exclusion criteria

A potential subject who meets the following criterium will be excluded from participation in this study:

- Pregnancy
- Newly diagnosed malignancy, with the exclusion of non-melanoma skin cancer, in the previous 6 months
- Chemotherapy or immunotherapy for malignancy
- Admission to hospital or rehabilitation center

### 4.4. Sample size calculation

Patients with type 1 and type 2 diabetes mellitus are eligible for participation. HbA1c is the primary outcome parameter. Blood for HbA1c will be collected at home by a fingerprick and send to the LUMC. This is a method to obtain insight in glycemc control that many patients perform, and prefer, in clinical practice as it saves them a visit to the hospital. The clinical laboratory in the LUMC is set up to analyse these samples. But this method, which is appropriate in the context of social distancing and limiting hospital visits during this COVID-19 outbreak, also has some consequences regarding the number of patients that need to be approached. From clinical practice we know that not all patients carry out the blood sampling in an appropriate way, despite clear instructions. Also the duration in the postal service renders some samples not suitable for analysis. In this COVID-19 period the postal service

may take longer than normal. Based on our experience from clinical practice and the current COVID-19 situation we estimate that 20% of samples cannot be analysed for HbA1c. The aim is to detect a difference in HbA1c of 4.0 mmol/mol (standard deviation 11 mmol/mol) in comparison to the HbA1c prior to the period of quarantine, which is considered to be clinically relevant in our population of patients with often well regulated diabetes. For an alpha error of 0.05 and a power of 90%, the minimum sample needed is 159 patients per patient group (type 1 and type 2 diabetes). Taking in consideration an estimated response rate of 35% and an estimated proportion of 20% of HbA1c missing measurements as a result of logistical, practical or technical problems, 568 patients per patient group (type 1 and type 2 diabetes) will be invited to participate. This is a total of 1136 patients. The numbers of participants mentioned above are much higher than the number that is minimally needed (15 per variable) to calculate the hierarchical regression analyses (see statistical analyses) on secondary outcomes.

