## 10. STATISTICAL ANALYSIS

- Categorical data: gender, level of education, type of diabetes, medication use, type of blood glucose measurements (fingerprick or glucose sensor (FGM/CGM)) will be presented by percentage and standard deviation (SD).
- Continuous variables: age, BMI, weight, height, HbA1c will be presented using the mean and the standard deviation (SD). Derived parameters: BMI will be calculated from height (m) and weight (kg) using the formula  $(\text{weight (kg)} / (\text{height (m)})^2)$  and will be presented as continuous variable by mean and standard deviation (SD). Glucose variability will be calculated by the standard deviation of the glucose values from the continuous and flash glucose monitors obtained during the previous week in the quarantine period. This SD will be compared to the SD from the glucose values during the last non-quarantine week. Other glyceic measures include time spent in range 4.0-10.0 mmol/l, time spent in hypoglycaemia (<3.0, 3.0-3,5, and 3.5-3.9 mmol/l), time spent in hyperglycemia ( $\geq 10.0$  mmol/l)
- Missing data will be excluded from analyses.

- Data will be statistically analysed using STATA intercooled 16.0. HbA1c measurements and SD measurements prior to and after the quarantine period will be compared using a paired-sample t-test in case of normal distribution or Wilcoxon Signed Rank Test in case of abnormal distribution. Furthermore, differences in HbA1c and glucose variability between patients with type 1 and type 2 diabetes will be measured using independent T-tests. Differences in well-being, distress and self-management between patients with type 1 and type 2 diabetes will be analysed using independent T-tests. The association between glucose variability and parameters for distress, well-being and self-management will be analysed using multivariate regression analysis.

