### 10.1. Primary study parameter(s)

#### **HbA1c**

HbA1c will be assessed in whole blood obtained by a fingerprick. The HbA1c will be compared to the last HbA1c in the non-quarantine period.

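### The 159 patients per group in section 4.4 match an unpaired two-sample calculation, but the primary HbA1c comparison is paired and the SD of 11 is not defined, so the stated 90% power is not that of the planned test

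*Protocol*

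**What the plan says.** Section 4.4 of the protocol sets the target: "The aim is to detect a difference in HbA1c of 4.0 mmol/mol (standard deviation 11 mmol/mol) in comparison to the HbA1c prior" to quarantine. With alpha 0.05 and 90% power it concludes that "the minimum sample needed is 159 patients per patient group (type 1 and type 2 diabetes"). Allowing for a 35% response and 20% missing HbA1c measurements, it then arrives at 568 invitations per type. It names no formula, does not say what the SD of 11 describes, and gives no correlation between the earlier and the later HbA1c.

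The analysis sections describe a within-patient comparison. Section 10: "HbA1c measurements and SD measurements prior to and after the quarantine period will be compared using a paired-sample t-test", with the Wilcoxon signed rank test as the alternative if the data are not normal. Section 10.1: "The HbA1c will be compared to the last HbA1c in the non-quarantine period".

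Two further statements affect how many pairs there will be. Section 3 says that the earlier HbA1c values "will be retrieved from the electronic health record of each patient, if available", and section 10 says "Missing data will be excluded from analyses".

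**The concern.** A sample size for a before-after comparison depends on the SD of the within-patient change. The SD of a single HbA1c value serves only together with the correlation between the two measurements. Section 4.4 supplies one SD without saying which it is, and its answer coincides with the formula for two separate groups of patients. The minimum and the 90% power are presented as properties of the primary test, yet they follow from its inputs only in a special case.

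At stake is what the study can be said to detect. If the usual positive correlation holds, or if 11 already is the SD of change, the study can detect changes well below 4.0 mmol/mol, and a null result would say more than section 4.4 implies. The margin available to absorb missing earlier HbA1c values is also unknown until the SD is defined.

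**Working it through.** **Inputs.** From section 4.4: difference 4.0 mmol/mol, SD 11 mmol/mol, alpha 0.05 (taken as two-sided), power 90%, response 35%, missing 20%. From sections 10 and 10.1: paired t-test of quarantine HbA1c against the last earlier HbA1c. Not in the document and therefore assumed: the correlation r between the two values (range 0 to 0.8) and the share of patients without an earlier value (10 to 30%).

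**1. Reproducing the plan's figures.** The sum of the normal quantiles is 1.9600 + 1.2816 = 3.2415.

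- Two independent groups, per group: 2 × (3.2415 × 11/4.0)² = 158.92, rounded up to 159. This is the stated figure. (The t-based version gives 160.)
- Invitations: 159/(0.35 × 0.80) = 567.9, rounded up to 568, also as stated.
- Other settings of the unpaired formula do not fit: one-sided alpha 0.05 gives 130, and two-sided alpha 0.025 gives 188.

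**2. Paired test, if 11 is the SD of the change.** (3.2415 × 11/4.0)² = 79.46, so 80 pairs by the normal formula and 82 by the noncentral t distribution. With 159 pairs, power for 4.0 is 99.5%. The change detectable with 90% power is 3.2415 × 11/√159 = 2.83 mmol/mol (2.85 by noncentral t).

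**3. Paired test, if 11 is the SD of a single HbA1c.** The SD of the change is 11 × √(2(1 − r)). All results below are by noncentral t.

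| Assumed r | SD of change | Pairs needed for 90% power | Power for 4.0 with 159 pairs | Detectable at 90% power with 159 pairs |
|---|---|---|---|---|
| 0 | 15.56 | 161 | 89.7% | 4.02 |
| 0.3 | 13.02 | 114 | 97.1% | 3.37 |
| 0.5 | 11.00 | 82 | 99.5% | 2.85 |
| 0.7 | 8.52 | 50 | >99.9% | 2.20 |
| 0.8 | 6.96 | 34 | >99.9% | 1.80 |

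In reverse, 159 pairs correspond to 90% power for 4.0 by the normal formula when the SD of change is 4.0 × √159/3.2415 = 15.56. That equals 11 × √2, which is the case r = 0.

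**4. Missing earlier HbA1c.** If 159 patients have a usable new sample and 10, 20 or 30% of them have no earlier value, then 159 × 0.9, 0.8 or 0.7 leaves 143, 127 or 111 pairs. Power for 4.0 is then:

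| Basis | 143 pairs | 127 pairs | 111 pairs |
|---|---|---|---|
| SD of change 11 | 99.1% | 98.2% | 96.7% |
| SD of HbA1c 11, r = 0.3 | 95.5% | 93.0% | 89.4% |
| SD of HbA1c 11, r = 0 | 86.3% | 82.0% | 76.6% |

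**The case against.** The strongest reply is that nothing is lost. On every basis in section 3 of the working, 159 complete pairs give about 90% power or more for 4.0 mmol/mol, so as a number of patients it is sufficient. This stands, and it limits the point to a misstated justification. It does not make the paragraph correct: 159 is called the minimum needed, and it is about twice the paired requirement if 11 is the SD of change.

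Second, the protocol names no formula, so the unpaired basis is inferred from the numerical match. The same 159 results from the paired normal formula with SD 11 per measurement and r = 0, so a deliberately cautious choice cannot be excluded. That is fair, but section 4.4 does not say so, and zero correlation between two HbA1c values from one patient would need to be declared as an assumption.

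Third, 159 per type might have been meant for the comparison of type 1 with type 2, since section 10 also says that "differences in HbA1c and glucose variability between patients with type 1 and type 2 diabetes will be measured using independent T-tests". An independent t-test with 159 per type does have 90% power for a difference of 4.0 at SD 11. But section 4.4 defines the 4.0 against earlier HbA1c, and section 2 lists the between-type comparison as secondary, so this reading does not rescue the text.

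Fourth, the missing-value rates are assumed. Section 8.3 plans retrieval for each patient without the qualifier in section 3, participants are already in care at the clinic, and the 20% allowance is worded broadly at its second mention. This stands: the lowest power figures are a sensitivity range, and they also need r at or near zero.

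**Conclusion.** The point holds. The stated minimum and the stated 90% power do not belong to the planned paired test as described. If 11 is the SD of change, the requirement is 82 pairs per type, and 159 pairs give 99.5% power whatever the correlation. If 11 is the SD of a single HbA1c, the stated figures are about right only at zero correlation.

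The error is conservative. With 159 complete pairs, power exceeds 90% at practically any positive correlation: 4.02 × √(1 − r) falls below 4.0 once r passes about 0.01. The primary test remains valid, and the study is not undersized for 4.0 unless many earlier values are missing and the correlation is low. What the reader cannot learn from section 4.4 is how much smaller a change the study can detect, or how much loss of pairs it can bear.

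This should be corrected, as an error in the justification and not as a threat to the result. The conclusion rests on a two-sided alpha and on the SD of 11 as stated. The correlations and the missing-value rates are assumptions, shown as ranges.

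**What to change.** Reword the sample size paragraph in section 4.4:

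1. State whether 11 mmol/mol is the SD of the within-patient change or of a single HbA1c value. In the second case, give the assumed correlation and its source.
2. Give the number of pairs that the paired test needs on that basis, and state that alpha is two-sided.
3. State what 159 pairs per type deliver. If 11 is the SD of change, for example: about 99.5% power for 4.0 mmol/mol, or 90% power for about 2.8 mmol/mol. If 159 was kept as a deliberately cautious number, say so.
4. Say whether the 20% allowance also covers patients without an earlier HbA1c on record.

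Keep 159 patients and 568 invitations per type. The surplus over the paired requirement protects against pairs lost because no earlier value exists, for which the calculation 159/(0.35 × 0.80) has no separate term. The cost is one reworded paragraph, with no change to recruitment or to the analysis.
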